10.3 Causality assessment

The Site PI will determine the relationship of adverse events to the research intervention using the following scale:

- Definite = AE is clearly related to the study procedures
- Probable = AE is likely related to the study procedures
- Possible = AE is possibly related to the study procedures
- Unlikely = AE is doubtfully related to the study procedures
- Unrelated = AE is clearly not related to the study procedures

Additionally, AEs will be considered “probably related” to study procedures if one of the following happens:

- Local anesthetic toxicity or allergy

10.4 Procedures for recording and reporting adverse events

All serious adverse events that occur from the time the subject provides informed consent through and including 28 calendar days after the procedure will be recorded. Non-serious adverse events that occur from the time the study procedures begin to the end of the last study visit will be recorded.

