10.1 Adverse event definitions	15
10.2 Severity assessment	16
10.3 Causality assessment	16
10.4 Procedures for recording and reporting adverse events	16
10.5 Other reportable events	16
11. Trial safety monitoring	17
11.1 Data Safety Monitoring Committee	17
12. Administrative requirements	18
12.1 Good clinical practice	18
12.2 Data quality assurance	18
12.3 Study monitoring	18
12.4 Ethical consideration	18
12.5 Patient confidentiality	18
12.6 Investigator compliance	18
12.7 Subject cost and payment	19
13. Funding sources	19
14. Publication Policy	19
References	20

Schedule of activities

	Screening/ Recruit/ Procedure Visit 1	PACU Visit 2	24 hours Post-op Visit 3	48 hours Post-op Visit 4 (Inpatient/ Phone)	7 days Post-op Visit 5 (Phone)
Window	Morning of Surgery	Following surgical procedure	24 hours post-op +/- 6 hours	48 hours post-op +/- 6 hours	7 days post-op +/- 6 hours
Screening and Eligibility	X				
Informed Consent	X				
Demographics	X				
Medical History	SOC				
Randomization	X				
Quadratus Lumborum Block	X				
Standard Medical Management	SOC				
Numbness Testing ¹		X			
Pain Questionnaire ²		X	X	X	X
Concomitant Medications ³	SOC	X	X	X	X
Adverse Events	SOC	SOC	X	X	X

¹Temperature sensation will be examined using a cold sensory technique

² Pain at rest, pain with activity, opioid consumption, nausea, location of most severe pain and satisfaction with regional anesthesia technique will be assessed

³Medications that are taken at home regularly and prior to arrival on the day of surgery, surgery premedication, and all medications for nausea and pain will be recorded.

List of abbreviations and definitions

AE	Adverse event
DSMC	Data Safety Monitoring Committee
PACU	Post-Anesthesia Care Unit
POD	Post-Operative Day
QLB	Quadratus Lumborum Block
SAE	Serious Adverse Event

1. Introduction

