The patient will be contacted via phone at 24 hours, 48 hours, and 7 days to assess satisfaction with regional anesthesia, pain at rest, pain with activity, opioid consumption, nausea, pain disturbing sleep, and location of most severe pain. Duration of hospitalization will be obtained from review of medical record. Subjects with new or persistent complaints at 7 days post-surgery that could be related to the study procedures will be offered continued follow-up by telephone. Follow-up procedures would depend greatly on the clinical presentation but could include imaging, specialist consultation or surgical intervention. Subjects without complaints will be given appropriate information for contacting the research team if such complaints arise.

Concomitant Medications:

Analgesic and anti-emetic requirements for block placement, intraoperatively, and in PACU will be extracted from the patient's electronic medical record.

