10.1 Adverse event definitions

Adverse event (AE)

An adverse event is defined as any untoward or unfavorable medical occurrence in a human subject including any abnormal sign, symptom, or disease temporally associated with the QLB or study procedure that appears or worsens during the study or study follow-up period. AEs may be anticipated (e.g., redness/soreness at injection site) or unanticipated (e.g., bleeding/infection/nerve damage).

Adverse event information will be collected throughout the study from informed consent through resolution of the AE and documented on the case report form or the standard follow-up questionnaire.

All AEs (anticipated and unanticipated) will be recorded on one of the study data sheets (case report form or standard questionnaire) by a study investigator or study staff. In the event of an unanticipated AE, the primary anesthesia team caring for the subject will intervene as deemed appropriate. These are the same provisions that would be made for any non-study case and represents standard practice.

Serious adverse event (SAE)

A serious adverse event is defined as any adverse event that meets one of the following criteria:

- Results in death; OR
- Is life-threatening; OR
- Requires hospitalization or prolongs existing hospitalization; OR
- Results in significant or persistent disability or incapacity; OR
- Results in a congenital anomaly/birth defect.

Given the minimal risk associated with the performance of QLB and the study procedures, no serious adverse events (SAEs) are anticipated. If a SAE occurs, the study primary and co-primary investigators will be immediately notified and further enrollment in the study will be halted until a full explanation of the cause of the event and its relationship to the QLB and/or study procedure is understood. The IRB will be notified and re-initiation of study enrollment will not occur until approved by the IRB.

Unanticipated problem (UP)

An unanticipated problem is defined as an event that meets all of the following criteria:

- 1) Unexpected in severity, nature, or frequency given the research procedures and the characteristics of the subject population (i.e., problems that are not described in this protocol or other study documents); AND
- 2) Related or possible related to participation in the research; AND
- 3) Suggests that research places subjects or others at a greater risk of harm related to the research than was previously known or recognized.

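### All SAEs are to be recorded to day 28, but after the day-7 call no contact or record check is scheduled for every subject, so days 8 to 28 are covered only passively or selectively

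*Combined protocol and SAP*

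**What the plan says.** Section 10.4 sets two recording windows. For SAEs it covers all events from informed consent "through and including 28 calendar days after the procedure will be recorded". For non-serious events it runs "from the time the study procedures begin to the end of the last study visit will be recorded". The SAE window is thus written to outlast the visits.

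The schedule of activities ends at Visit 5, a telephone visit at "7 days post-op +/- 6 hours". That column is also the last one marked for adverse events.

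Section 7, in the follow-up paragraph, names the same contacts: "The patient will be contacted via phone at 24 hours, 48 hours, and 7 days to assess" pain, opioid use, nausea and related items. For the time after day 7 it gives two routes:

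- Subjects with new or persistent complaints at day 7 "that could be related to the study procedures will be offered continued follow-up by telephone". No duration or end date is given.
- For everyone else: "Subjects without complaints will be given appropriate information for contacting the research team if such complaints arise".

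The only record review named in that paragraph is for length of stay: "Duration of hospitalization will be obtained from review of medical record". Section 7.1 lists what is extracted from the records (identifiers, demographics, pain, opioid use, ASA class) and does not include readmissions or SAEs.

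Section 10.1 attaches a consequence to any SAE: "further enrollment in the study will be halted until a full explanation of the cause of the event" and its relationship to the block or study procedure is understood, with restart only on IRB approval.

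**The concern.** The plan states a 28-day SAE window but describes procedures that look for events in every subject only up to day 7. A subject who is well at the day-7 call and is admitted on day 12 has an SAE under section 10.1, because hospitalization alone makes an event serious. Section 10.4 requires that event to be recorded. Yet a team that followed the plan to the letter would learn of it only if the subject chose to call.

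Two things are at stake. The first is the safety rule: the enrollment halt acts on SAEs the team knows about, and section 11.1 says there is no standing monitoring board to look elsewhere. The second is what can be claimed afterwards. An SAE count to day 28 would rest on active questioning for the first week and on volunteered information for most subjects after that, and the two should not be reported as one uniform ascertainment period.

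**Working it through.** **Inputs**

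- End of SAE window: day 28 after the procedure (section 10.4).
- Last scheduled contact: day 7, plus or minus 6 hours, so 6.75 to 7.25 days (schedule of activities).
- Planned enrollment: 48 (sections 3 and 8.1).

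The 28-day window is a design choice, so there is no calculated figure of the plan's own to reproduce.

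**Share of the post-procedure window with no scheduled contact**

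Share = (28 − day of last scheduled contact) / 28

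- Contact at day 7: (28 − 7)/28 = 21/28 = 75.0%
- Contact at 6.75 days: 21.25/28 = 75.9%
- Contact at 7.25 days: 20.75/28 = 74.1%
- Counting calendar days 0 to 28 as 29 days: 21/29 = 72.4%

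Three quarters is a fair summary under any of these counts.

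**Does any described route find new SAEs in every subject on days 8 to 28?**

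| Route | Where | Why it does not cover all subjects |
|---|---|---|
| Continued telephone follow-up | Section 7 | Needs a complaint at day 7 that might be related to study procedures; it is an offer, with no stated duration |
| Subject contacts the team | Section 7 | Passive; in context it invites calls about possibly related complaints |
| AE collection through resolution | Section 10.1 | Follows events already known; names no later visit or record check |
| Weekly review by the principal investigator | Section 11.1 | Works on events already reported |
| Review after 15 subjects, and later data reviews | Sections 11.2 and 12.3 | Work on data already collected |
| Record review in follow-up | Section 7 | Named for length of stay only |

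Relatedness matters here. Section 10.4 asks for all SAEs, and the causality scale in section 10.3 includes an unrelated category, so unrelated events are meant to be collected. Both post-day-7 routes in section 7 turn on possible relatedness. An admission that the subject regards as having nothing to do with the block falls outside them.

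**Effect of a day-28 check.** If every subject has a scheduled record check and question once day 28 has passed, the part of the window with no scheduled ascertainment falls from 21 of 28 days to 0 of 28. No sample-size or power figure changes.

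**The case against.** The strongest reply is that section 10.4 is a recording rule and does not guarantee detection. It ends the non-serious window at the last visit and deliberately lets the SAE window run on, so that serious events the team happens to learn of are still written down. A recording window longer than the visit schedule is not in itself a contradiction. This stands in part: the text can be read that way. But section 10.4 says all SAEs, and the plan does not say how those after day 7 are to come to the team's notice. That needs to be stated even on the milder reading.

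A reader might infer that no contact at all is planned after day 7, or that days 8 to 28 are wholly unobserved. The documents do not support this. Section 7 offers continued calls to some subjects and gives the rest a way to report. These routes are selective or passive, but they exist.

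A reader might also infer that reporting would differ by arm, since the block is given in the holding area and no sham or blinding of subjects is described. That is possible but not shown. The follow-up routes make no distinction by arm, and no between-arm analysis of adverse events is specified. It is a reason to make any added check identical in both arms; it does not establish bias.

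Finally, section 9.1 calls block-related adverse effects extremely rare and section 10.1 anticipates no SAEs. Neither gives an all-cause rate for days 8 to 28 after this surgery, so they do not show that the period is empty of SAEs.

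**Conclusion.** The point holds in a limited form. After the day-7 call there is no scheduled contact or SAE record check for all subjects, so SAEs on days 8 to 28 (21 of 28 days, 75%; 74.1% to 75.9% across the visit window) are captured only passively or selectively. As a result, the enrollment halt in section 10.1 may not be triggered by a late SAE.

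This rests on the schedule of activities and section 7 being the full description of follow-up, and on taking the word all in section 10.4 at face value. It does not extend to an estimate of how many SAEs would be missed. The documents give no rate, and a calculation from an assumed risk would give the chance that an SAE occurs, which is not the chance that its detection depends on self-report. The POD1 primary outcome is not affected. This is a gap in safety ascertainment that is cheap to close.

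**What to change.** Add a day-28 row to the schedule of activities, for both arms, with two elements:

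- a medical-record check for readmission, emergency visit, reoperation and death;
- one scripted question, by phone or message, asking about any such event whether or not the subject thinks it is related. This also reaches care given elsewhere that the local record may not show.

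Both should be done identically by arm and once day 28 has passed, so that the whole window is covered. Section 10.4 should then refer to this check as the means of collecting SAEs after the last visit.

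Shortening the SAE window to day 7 would make the text consistent but is not recommended. It would remove the duty to record an SAE that the team learns of on, say, day 15, and so weaken the safeguard in section 10.1.

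The cost is a few minutes per patient for 48 patients, by staff who already extract records and make the follow-up calls, plus an amendment with written IRB approval before use (section 12.6).

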After completion of pre-operative check in and consent is obtained by the staff anesthesiologist, the subject will be randomized to receive or not receive QLB. Randomization will be determined by opening a sequential, pre-sealed envelope with the group assignment designated within. If assigned to the intervention arm, they will then be prepped for QLB.

Quadratus Lumborum Block Procedure:

The block will be performed in the preoperative holding room as is standard practice at UW Health at the American Center. An intravenous catheter will be placed, and the subject will be pre-medicated with midazolam and/or fentanyl as needed at the discretion of the staff anesthesiologist.

Quadratus lumborum blockade will be performed after positioning the patient in the lateral decubitus position with the assistance of ultrasound guidance in the mid-abdomen posterior to the mid-axillary line. A Stimuplex needle (B. Braun Medical Inc., Melsungen, Germany) will be inserted in-plane to the ultrasound probe until the tip of the needle is appropriately positioned. Thirty milliliters of 0.25% bupivacaine will be injected under ultrasound guidance after negative aspiration. The procedure will then be repeated on the opposite side, maintaining sterility and, again, injecting 30 mL of 0.25% bupivacaine. The Bupivacaine mixture will be mixed with 2.5mcg epinephrine/ml of solution as an intravascular marker which is standard in most peripheral nerve blocks. In a situation where a patient is less than 60kg, a weight-based adjustment will be made to adjust dosing to the clinically accepted standard of 0.25mg/kg of bupivacaine. In the rare event that sonographic views are unobtainable, the patient will be excluded from the study. This outcome is unlikely to be clinically significant as qualification for laparoscopic ventral hernia repair has its own cutoff for body mass index and blocks are very rarely abandoned. However, for patient safety, we reserve the right to abandon a block.

During the Surgical Procedure:

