7.2 Subject withdrawals

At any point prior to or during the intervention period, the subject's clinical care team or a study physician may decide the subject should be withdrawn from the study. Additionally, a subject may at any point elect to withdraw themselves from the study. If a subject is withdrawn from the study for any reason the subject will then be followed according to standard of care follow-up.

Study intervention will immediately stop and subject's clinical care team and a study physician will be immediately notified if the subject suffers a severe adverse perioperative outcome.

In the event the study method is terminated, the reason for termination will be documented on a case report form.

8. Data analysis and statistical considerations

All data will be summarized using standard descriptive statistics, including mean, standard deviation, minimum, maximum, median, inter-quartile range, and confidence intervals, as appropriate. The data will be presented graphically (where possible) using scatter plots, profile plots, or histograms. Data analyses will be performed on an intent-to-treat basis based upon assignment to a treatment arm using SAS (SAS Institute Inc., Cary, NC; version 8.2 or greater) or other statistical software. The primary analysis will consist of comparing the two groups for superiority. For all tests, statistical significance will be defined as a p-value less than 0.05. Repeated measures ANOVA will be used to analyze comparisons made across multiple time points. Patients with missing longitudinal data will be handled by either using data imputation methods to replace the missing data or via alternative analyses tolerant of missing data values. Holm-Bonferroni correction will be used to control familywise error rates for comparisons across multiple time points.

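### Sections 10.1 and 10.4 give different recording windows for non-serious adverse events, and the protocol does not secure adverse-event follow-up or reporting after withdrawal, post-randomisation exclusion or an abandoned block

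*Combined protocol and SAP*

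**What the plan says.** Five parts of the protocol bear on this.

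- **Section 10.1** (definitions): "Adverse event information will be collected throughout the study from informed consent through resolution of the AE", and "All AEs (anticipated and unanticipated) will be recorded on one of the study data sheets". It does not separate serious from non-serious events.
- **Section 10.4** (recording and reporting): serious adverse events (SAEs) occurring "from the time the subject provides informed consent through and including 28 calendar days after the procedure will be recorded"; for the rest, "Non-serious adverse events that occur from the time the study procedures begin to the end of the last study visit will be recorded".
- **Section 7.2** (withdrawals): "If a subject is withdrawn from the study for any reason the subject will then be followed according to standard of care follow-up". After a severe perioperative outcome, "Study intervention will immediately stop and subject's clinical care team and a study physician will be immediately notified". The reason for terminating the study method goes on a case report form.
- **Section 7** (block procedure): the block is done on one side and then "The procedure will then be repeated on the opposite side". It comes after randomisation. A subject whose sonographic views cannot be obtained is excluded from the study, and the team may abandon a block for safety. No AE follow-up is stated for either case.
- **Section 11.1** (safety monitoring): data from a subject who withdraws early are left out of the final study.

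In the Schedule of Activities, the AE row reads SOC on the day of surgery and in PACU, and X (a study activity) at 24 hours, 48 hours and 7 days.

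**The concern.** Two recording rules for the same events invite inconsistent data capture. A non-serious event between consent and the first study procedure is recorded under 10.1 but not under 10.4.

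The larger issue is what happens to subjects who leave the planned path after being exposed to the block. Section 1.1 describes laparoscopic repair as typically outpatient surgery, so the three later contacts are the main way the study would learn of a delayed haematoma, infection or sensory deficit. If those contacts lapse on withdrawal, such an event may never be seen. If it is seen, 11.1 may still keep it out of the reported results. The subjects affected could include those in whom the block went badly, so the losses would not be random with respect to safety. The 15-subject safety review in Section 11.2 also depends on what has been recorded.

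**Working it through.** **1. The windows side by side**

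| Source | Events | Start | End |
|---|---|---|---|
| 10.1 | All AEs | Informed consent | Resolution of the event |
| 10.4 | SAEs | Informed consent | Day 28 after the procedure |
| 10.4 | Non-serious AEs | Start of study procedures | Last study visit (Visit 5, day 7 ± 6 hours, on the schedule) |
| 7.2 | Withdrawn subjects | Not stated | Not stated |

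The start for non-serious AEs conflicts outright. The ends need not conflict: 10.4 limits when an event must occur, and 10.1 can be read as saying how long information on it is then collected.

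**2. A non-serious event that begins after withdrawal**

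The term for the last study visit in 10.4 is not defined for a withdrawn subject.
- If it means the last visit attended, an event starting later falls outside 10.4.
- If it means Visit 5, the event should be recorded, but 7.2 has moved the subject to standard-of-care follow-up. On the schedule's own labels, that does not include the three AE checks.

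Neither reading secures a study contact at which the event would be found. Section 7 offers continued telephone follow-up for complaints at 7 days, which does not clearly reach someone already withdrawn.

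**3. An SAE after withdrawal**

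Section 10.4 makes no exception for withdrawal, so recording to day 28 is still required. For any subject, the last scheduled contact is day 7, which leaves 28 − 7 = 21 days without one. For a withdrawn subject, the three earlier checks are not secured either.

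**4. Exclusion and abandonment**

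If views fail on the first side, no local anaesthetic has been given. If they fail on the second side, the first has already been injected, so the subject is exposed and, as written, excluded. An abandoned block may also leave a subject partly exposed, and that subject's later status is not stated.

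**5. Size**

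- The plan's sample size reproduces. A two-sided t-test (sidedness assumed), difference 2, SD 2.2, alpha 0.05 and power 80% gives 20.0016 per group, rounded up to 21.
- Section 8.1 enrols 24 per group, so the loss allowance is 24 − 21 = 3 per group.
- One missed complication among 24 block subjects: 1/24 = 4.2% becomes 0/24 = 0%.
- Share of the block group without secured study AE checks if 1 to 3 are affected: 1/24 = 4.2% to 3/24 = 12.5%.

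These are illustrations. The documents give no expected number of withdrawn, excluded or abandoned-block subjects.

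**The case against.** The case for leaving the text alone is that 10.1 and 10.4 work together, 7.2 is merely silent, and the consent pages, which are not available here, may cover contact after withdrawal. Several parts of this stand, and they rule out stronger conclusions that a reader might draw.

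- *That 7.2 sets a third, conflicting end point.* It sets none. It only says what kind of follow-up a withdrawn subject receives.
- *That an event prompting withdrawal goes unrecorded.* Such an event has already occurred. Section 10.1 records all AEs, 10.4 records SAEs to day 28, and 7.2 documents the reason for termination. A known SAE would also still trigger the enrolment halt in 10.1. What is not secured is continued study follow-up of that event and detection of later ones.
- *That a severe outcome or an abandoned block forces withdrawal.* Section 7.2 stops the intervention and notifies physicians; withdrawal by clinicians is discretionary. Only unobtainable views are said to lead to exclusion, and the intent-to-treat statement in Section 8 points towards keeping a subject whose block was abandoned.
- *That reported complication rates will be too low.* This depends on an event occurring in such a subject and being missed or dropped. The allowance of 3 per group covers drop-out and non-completion generally and does not estimate exposed subjects lost to safety follow-up.

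Two things remain. The starting points for non-serious AEs do conflict. And 7.2 is not neutral once read with the schedule, because the later AE checks are labelled as study activities. Section 11.1 adds an explicit exclusion of data that a silent consent form would not undo.

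**Conclusion.** The point holds in two parts. First, 10.1 and 10.4 disagree on when recording of non-serious AEs starts, and they leave the relation between their ends to be inferred. Second, the protocol does not secure AE follow-up after withdrawal, post-randomisation exclusion or an abandoned block, and 11.1 can remove events from the reported results even where they were recorded.

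All three later AE checks are unsecured for a withdrawn subject. The effect on reported rates is conditional: in a group of 24, a single missed complication is the difference between 4.2% and none.

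This rests on three assumptions: that the schedule's SOC and X labels mean what they appear to mean; that the consent form does not already provide for safety contact after withdrawal; and that 11.1, which speaks of a subject who withdraws, also covers subjects withdrawn by clinicians. If 11.1 covers only subjects who withdraw themselves, the reporting loss is narrower but the follow-up gap is unchanged. The correction should be made, because it is specific and cheap and bears directly on safety ascertainment.

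**What to change.** 1. Reconcile 10.1 and 10.4: one start for AE recording, one stated onset window for each class of event, and an explicit statement that ongoing events are followed to resolution. Define the last study visit for a subject who leaves early.
2. In 7.2 and Section 7, state that any randomised subject who is withdrawn, is excluded after randomisation or has an abandoned block keeps the AE questions at the planned 24-hour, 48-hour and 7-day contacts, and stays within the 10.4 SAE window, unless the subject refuses contact.
3. Amend 11.1 so that all subjects exposed to any part of the block appear in the safety tables, whether or not they were withdrawn. Without this, 11.1 would contradict the other two changes.

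Clinical treatment of any event stays with the care team.

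The cost is wording in 7, 7.2, 10.1, 10.4 and 11.1, with IRB approval under Section 12.6, and a few calls that are already planned. The downside is a slightly higher reported AE count.
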